#### Table 6-2:Phase 2 Assessments

Visit name	Screening	Cycle 1 (21 days; study Day 1-21; Week 1-3)			Cycle (21 da Week	2 ys; study 4-6)	y Day 22	-42;	Cycle (21 da Day 4 Week	3 ays; stud 13-63; 1 7-9)	ły	Cycle 4 (21 days) Cycles uj months (	) and all p to 48 4 years)	EOT u (up to 21 days after the last study dose)	Safety follow-up visit (90 days after the last study dose)	
Day of cycle	-28 to -1		CIDI	C1D8	CID15	- ALCO	1070	C2D8	C2D15	HUED	Ideo	C3D8	C4D1	and CXD1		
		pre-dose	post-dose			pre-dose	post-dose			pre-dose	post-dose		pre-dose	post-dose		
Obtain Informed Consent	x															
Obtain pharmacogenomic informed consent	x															
IXRS	x	Xª				Xª				Xª			Xa		х	
Demography	x															
Inclusion/ exclusion criteria	x	х														
Medical History b	х															
Height	х															
Weight	х	х				х				х			х		x	
Physical examination e	х	х				х				х			х		x	
Vital signs d	x	х	х			х	х			х			х		х	
ECOG performance	x	х				х				х			х		x	
Oxygen saturation test	x															
Cardiac markers e	х															
12-Lead ECG f	x	x	x							х	х				x	

Property of the Sanofi Group - strictly confidential

PAGE 97 OF 217

## Amended Clinical Trial Protocol 07

KY1044/SAR445256-KY1044-CT01/TCD17370 - alomfilimab

10-Nov-2021 Version number: 1

Visit name	Screening	Cycle 1 (21 days; study Day 1-21; Week 1-3)			Cycle (21 da Week	2 ys; study 4-6)	y Day 22	-42;	Cycle (21 da Day 4 Week	3 ays; stud 13-63; 17-9)	ly	Cycle 4 (21 days) Cycles uj months (	) and all p to 48 4 years)	EOT u (up to 21 days after the last study dose)	Safety follow-up visit (90 days after the last study dose)	
Day of cycle	-28 to -1		CIDI	C1D8	CID15	- C2D1		C2D8	C2D15	Max	Ideo	C3D8	C4D1	and CXD1		
		pre-dose	post-dose			pre-dose	post-dose			pre-dose	post-dose		pre-dose	post-dose		
Review AE	х	х	Х	х	х	х	х	Х	Х	х	х	х	х	х	x	х
Review Concomitant Medications	х	х				х				х			х		x	Х
Hematology	х	Xg		Xg	Xg	Xg		Xg	Xg	Xg		Xg	Xg		x	
Clinical Chemistry	х	Xg		Xg	Xg	Xg		Xg	Xg	Xg		Xg	Xg		x	
Fasting lipid profile h	х															
Coagulation (aPTT, INR)	х	X				Xg				Xg			X g		x	
HbA1c i	х														x	
Urinalysis j	х	х				х				х			х		x	
Pregnancy test k	х	х				х				х			х		х	
Thyroid function 	х									х					x	
Viral testing, HIV, HBV, HCV m	х															
Auto-Abs n	х					х							х		х	
Anti-KY1044 and Anti-atezolizumab (ADA)°		x				x				x			x			x
PK (KY1044) p		х	Х			х	х			Х	Х		х	х	х	х
PK (atezolizumab) p		х	х			х	Х			Х	х		х	X	x	x

Property of the Sanofi Group - strictly confidential

PAGE 98 OF 217

## Amended Clinical Trial Protocol 07

KY1044/SAR445256-KY1044-CT01/TCD17370 - alomfilimab

10-Nov-2021 Version number: 1

Visit name	Screening	Cyc (21 Day	days; 1-21;	study Week	: 1-3 )	Cycle (21 da Week	2 iys; study 4-6)	y Day 22	-42;	Cycle (21 da Day 4 Week	e 3 ays; stud 13-63; 1 7-9)	ły	Cycle 4 (21 days) Cycles uj months (	) and all p to 48 4 years)	EOT u (up to 21 days after the last study dose)	Safety follow-up visit (90 days after the last study dose)
Day of cycle	-28 to -1		CIDI	C1D8	CID15	- C2D1		C2D8	C2D15		C3D1	C3D8	C4D1	and CXD1		
		pre-dose	post-dose			pre-dose	post-dose			pre-dose	post-dose		pre-dose	post-dose		
RNA signature from PBMC (Nanostring)		x		x		x		x								
Fresh tumor biopsy q	x							х								
PBMC FACS or ChipCytometry analysis		x		x		x		x								
Plasma cytokine /chemokine panel		Х	X	х		х	Xt	х		х	х	х				
Serological tumor markers s	х	х				х				х			х		х	
Tumor Imaging RECIST 1.1t	х											х				
KY1044 administration v		х				х				х			х			
Atezolizumab administration (only for patients on combination therapy)		x				x				x			x			

A window of 3 days is permissible to complete Day 1 assessments, a window of 1 day is permissible to complete all other assessments

a IXRS contact can be performed prior to the patient Day 1 visit to receive treatment allocation.

b Medical History including date of diagnosis and extent of cancer, prior antineoplastic therapies (chemotherapies, targeted agents, radiation, surgery) and current concomitant medication (including SARS-CoV-2 vaccines).

c Complete physical examination should be performed at screening and at the EOT. This should also include a full dermatological examination (complete skin and mucosal exam). Abbreviated physical examination will be performed every cycle.

Property of the Sanofi Group - strictly confidential

PAGE 99 OF 217

Amended Clinical Trial Protocol 07 KY1044/SAR445256-KY1044-CT01/TCD17370 - alomfilimab

- d Vital signs: during Cycles 1 and 2, BP and HR will be monitored in the clinic every 15 minutes during the infusions of study treatment and every 30 minutes inbetween the infusions (for combination therapy), 60 min after the last infusion of study treatment. See Section 6.5.7.
- e Cardiac markers at screening will include: Baseline Troponin I for all patients. Additionally, N-terminal pro B-type natriuretic peptide (NT-pro-BNP) will only be taken for patients with a history of cardiac disease (according to exclusion criteria). Repeated assessments of cardiac markers during the study will be performed only when clinically indicated.
- f ECGs will be taken pre- and post-dose at Cycles 1, 3 and 6 as close as possible to each of the PK timepoints (see Section 6.5.8). In the event of abnormal ECG findings and if clinically indicated, an unscheduled PK sample should be collected and Troponin I, together with assessments for CK, CK-MB, AST and LDH. NT-pro-BNP should be measured together with the other cardiac markers as outlined above only in patients with previous cardiac complications at screening.
- g All samples will be analyzed centrally. On the occasions marked g only, duplicate samples for immediate access to key safety laboratory parameters (hematology, clinical chemistry and coagulation) will be analyzed at local labs as well.
- h At screening, clinical chemistry includes collection of a fasting lipid profile samplI.
- *i* HbA1c should be measured every 12 weeks throughout the study and will be assessed at EOT only if the previous assessment has not been performed within the last 3 months.
- *j* Urinalysis will include pH, protein, glucose, ketones, blood and urine dipstick pregnancy test.
- k Serum pregnancy test ( $\beta$ -HCG) will be performed on screening. Urine dipstick test will be performed at all other visits.
- / Thyroid function includes free T4 and TSH and the analyses will be repeated every 3 cycles and at EOT.
- *m* Virology testing will be performed at screening for HIV, HBV and HCV. In patients, who are known to be positive for HBV and HCV, tests will be repeated every cycle pre-dose and a confirmatory sample should be taken when clinically indicated. See Section 6.5.9 for more details.
- *n* Auto-antibodies include: anti-DNA, anti-nuclear, anti-mitochondrial and anti-phospholipid antibodies and Rheumatoid factor (RF) and acetyl-choline receptor antibodies (AChR). When a blood sample is positive for ANA (ie, titer>40) it will be tested for antibodies against extractable nuclear antigens. Samples for auto-antibody analyses will be collected at screening, every second cycle pre-dose for the first six cycles (C2, C4, C6), at EOT and then every 12 weeks up to 48 months of treatment and when clinically indicated.
- 0 ADA samples should be collected at every cycle on Day 1 and unscheduled at any time, when clinically indicated. For detailed ADA sample collection schedule see Section 6.4.2.
- p PK samples will be taken pre- and post-dose during all cycles and unscheduled at any time, when clinically indicated. For detailed PK analysis timings please refer to Section 6.4.2. Note: On days and timepoints when biomarker and pharmacokinetic blood samples are being collected, the PK sample must be drawn first. For further details please see schedule of PK assessments in Section 6.4.2.
- *q* Fresh tumor biopsy should be taken once other screening investigations strongly suggest the patient is likely to be eligible to avoid unnecessary risk of biopsy for a patient who is not going to be eligible. Where a prior (archival) biopsy is available no older than 3 months, the archival tissue may be substituted for a fresh tumor biopsy at screening. A fresh tumor biopsy is mandatory on treatment (C2D8). Where feasible, collection of a tumor biopsy at progression is encouraged.
- r Plasma sample for cytokine analysis post dose timepoint is 6 to 8 hours post-infusion on C1D1 and C2D1 and C3D1. Unscheduled sample may be collected if required.
- s Blood sample for measurement of serological tumor markers will be taken at screening, pre-dose of every cycle and EOT only for those patients that have tumors with correlative serological markers.
- t Tumor Imaging RECIST 1.1 assessment is done every 8 weeks ( $\pm$ 7 days) after the start of treatment for the first 16 weeks, after that every 12 weeks ( $\pm$ 7 days) for 48 months of treatment duration or until objective disease progression; visit window for assessment is  $\pm$ 7 days. In case of progression of disease without clear clinical signs of progression, the patient should continue treatment. In this case a confirmatory scan should be scheduled 4 to 8 weeks later as per iRECIST guidelines. The thorax CT/MRI scan performed at screening as part of the RECIST assessment will document the lung parenchyma status.
- *u* Please see Section 8.1 for details of follow up after end of treatment visit.
- v KY1044 is always to be administered first followed by a saline solution flush to empty the line as described in the pharmacy manual. For the combination part, a slow saline infusion will continue (after this saline flush) for approximately 1 hour before starting the atezolizumab infusion at the same infusion site. There should be a period of at least 1 hour after the infusion(s) are complete whereby the patient requires close observation as outlined in Section 5.2.2.

### 6.1 Screening Assessments

### 6.1.1 Written Informed Consent

Written informed consent for the study will be obtained from each patient before any protocol-specific procedures are carried out.

At the screening visit, the Investigator will explain the aims, methods, anticipated benefits and potential risks of participating in the study and should inform the patient that participation is voluntary and that they can withdraw from the study at any time. Each patient will be given a study-specific Patient Information Sheet to read as part of the informed consent process and will be given adequate time to ask questions. In accordance with ICH GCP and 21 Code of Federal Regulations (CFR) 50, informed consent shall be documented by the use of an Informed Consent Form (ICF) approved by the IEC/IRB. The ICF will be signed and personally dated by the patient, and by the site personnel responsible for obtaining consent.

In addition to the ICF for the study, the patient may be asked to participate in the pharmacogenomic sampling section of the study, for which there is a separate ICF and Patient Information Sheet. The importance of this assessment should be clearly outlined to all patients. The use of genomic test such as FoundationOne (Foundation Medicine Cambridge, MA, USA) may be conducted at a later stage to understand the molecular/mutanome profiling of the tumors in order to correlate response (or lack of response) with specific genomic profiles (eg, tumor mutation burden, EGFR status etc.). However, lack of informed consent to participate in the pharmacogenomic sampling section of the study does not preclude patients from participating in the clinical trial.

Informed consent procedure will be documented in the patient's medical records. The patient will be given a copy of the Patient Information Sheet and their signed and dated ICF, and the original ICF will be filed in the ISF.

#### 6.1.2 Screening and Enrollment into the Study

All screening assessments must be performed within the 28-day screening period. All screened patients will be allocated a unique screening number (See Section 5.9).

Assessment of inclusion and exclusion criteria must be checked during the screening period and finally confirmed prior to patient admission on C1D1. Emergency cards will be handed out to patients prior to first administration of IMP (IMPs). After receiving the first infusion in Phase 1, patients will be either hospitalized or remain in the clinic for at least 6 to 8 hours until the last assessments. They will be provided with instructions for after hour care per institutional standard and will return to the clinic on C1D2. In Phase 2, patients will be admitted prior to the first dose and will remain in the clinic for 6 to 8 hours after the first dose administration for all assessments to be performed.

#### 6.1.3 Screen Failures

A patient who signed an ICF but failed to be started on-treatment for any reason will be considered a screen failure. The reason for screening failure will be entered into the eCRF.

The demographic information, informed consent, and inclusion/exclusion pages must also be completed for screen failure patients. No other data will be entered into the clinical database

for patients who are screen failures, unless the patient experienced an SAE during screening or died or withdrew consent, when the appropriate eCRF pages should be completed.

### 6.1.4 Demographic Information

Demographic information will be collected at the screening visit as follows:

- Age
- Year of birth
- Sex
- Race
- Ethnicity

#### 6.1.5 Medical History

The Investigator will be responsible for review of the medical history of patients to ensure that they meet the criteria for eligibility for the study. Data to be collected will include relevant medical, surgical and radiation history and current medical conditions, diagnosis, including date and extent of tumor, details of prior anti-neoplastic treatments, current concomitant medication, SARS-CoV-2 vaccines, current significant non-drug therapies and other important molecular tumor characteristics. Medical history will be taken at screening and concomitant medications and vaccines, including SARS-CoV-2 vaccines, will be assessed throughout the study according to the schedules in Table 6-1 and Table 6-2.

For SARS-CoV-2 vaccinations, report the following in the appropriate pages of the eCRF:

- Information on each administration of SARS-CoV-2 vaccine. Each injection of SARS-CoV-2 vaccine must be reported as separate entries, including the vaccine name, dose and date of injection (Prior/Concomitant Medication eCRF).
- Any observed AE following administration of the SARS-CoV-2 vaccine during the study treatment period (Adverse Events eCRF).
- COVID-19 antibody titers, if measured after vaccination and available (Unscheduled Local Lab Results eCRF).

### 6.2 Assessment of Efficacy

#### 6.2.1 Tumor Assessments

Tumor response will be determined locally according to two sets of criteria:

- RECIST 1.1: Appendix 1 (51, 52)
- iRECIST: Appendix 2 (53)

The Investigator's assessment according to both RECIST 1.1 and iRECIST will be used for the analysis of response and for treatment decisions (study discontinuation due to progressive disease as per iRECIST). During the course of the study, the Sponsor may decide to have a central review of the radiological assessments performed. In such case, the Investigator's staff will be instructed on how to send data from these radiological assessments to a CRO for central review when needed.

RECIST 1.1 guidelines for measurable, non-measurable, target lesions (TLs) and non-target lesions (NTLs) and the objective tumor response criteria are presented in Appendix 1 of this protocol.

Screening tumor assessments will include CT of the thorax and abdomen (including liver and adrenal glands) and pelvis and should encompass all areas of known predilection for metastases in the disease under evaluation and will additionally investigate areas that may be involved based on signs and symptoms of individual patients. Brain magnetic resonance imaging (MRI) is mandatory for patients with known or suspected brain metastases.

If a patient is intolerant to iodine-based contrast agents, CTs may be performed without contrast. MRI may be used to evaluate sites of disease where a CT without IV contrast is not adequate or to evaluate sites of disease that are not adequately imaged by CT. Ultrasound should not be used to measure sites of disease.

Screening assessments should be performed no more than 28 days before the start of study treatment, and ideally should be performed as close as possible to the start of study treatment. Scans obtained as part of standard clinical practice, prior to informed consent, but within the 28-days prior to treatment are acceptable.

The methods of assessment used at screening should be used at each subsequent follow-up assessment every 8 weeks ( $\pm$ 7 days) after the start of treatment for 16 weeks, after that every 12 weeks ( $\pm$ 7 days) for 48 months of treatment of duration or until objective disease progression as defined by RECIST 1.1/iRECIST (see Table 6-3). Scans confirming progression should preferably not be conducted within 1 week of a progression biopsy to allow for reduction in inflammation.

Any other sites at which new disease is suspected should also be appropriately imaged. If an unscheduled CT/MRI scan is performed and the patient has not progressed, every attempt should be made to perform subsequent assessments at the scheduled visits whilst the patient remains on study treatment.

Procedure	Screening	During treatment/Follow-up
CT with (or without) contrast enhancement or MRI (Thorax, Abdomen, Pelvis)	Mandated	During treatment : Every 8 weeks (+7 days) for the first 16 weeks and then every 12 weeks until progression of disease as per iRECIST or patient withdrawal.
Brain CT or MRI with contrast	Mandated (for patients with known or suspected brain metastases)	If disease was detected at screening, or if clinically indicated.

 Table 6-3:
 Disease Assessment Collection Plan

CT=computed tomography; iRECIST=immune-related response evaluation criteria in solid tumors; MRI=magnetic resonance imaging

### 6.2.1.1 RECIST 1.1

Categorization of objective tumor response at each visit will be based on the RECIST 1.1 guidelines for response: CR, PR, SD and progression of disease. For ORR, a visit response of CR or PR must be confirmed by a later scan conducted at least 4 weeks after the initial response is observed.

Target lesion progression will be calculated in comparison to when the tumor burden was at a minimum (ie, smallest sum of diameters previously recorded on study). In the absence of progression, tumor response (CR, PR, SD) will be calculated in comparison to the baseline tumor measurements obtained before starting treatment.

If the Investigator is in doubt as to whether progression has occurred, particularly with response to NTLs or the appearance of a NL, it is advisable to continue treatment and reassess the patient's status at the next scheduled assessment or sooner if clinically indicated.

To achieve 'unequivocal progression' on the basis of non-target disease, there must be an overall level of substantial worsening in non-target disease such that, even in presence of SD or PR in target disease, the overall tumor burden has increased sufficiently to merit discontinuation of therapy. A modest 'increase' in the size of one or more NTLs is usually not sufficient to qualify for unequivocal disease progression status.

If repeated scans confirm progression, then the date of the initial scan should be declared as the date of progression.

All RECIST 1.1 assessment images will be reviewed at site. Duplicates may be collected, stored and can be sent for independent central RECIST 1.1 review, if deemed appropriate.

It is important to follow the assessment schedule as closely as possible. Please refer to the Schedule of Assessments see Section 6.

### 6.2.1.2 *iRECIST*

RECIST 1.1 has been modified to take into consideration the unique response kinetics which have been observed with immunotherapy in some patients where responses to immune therapies may occur after progression has been assessed (53). Therefore patients should be treated and followed up post initial progression until subsequent disease progression (confirmed progression). Note: patients with rapid tumor progression or with symptomatic progression that requires urgent medical intervention will not be eligible to continue to receive treatment.

In this study a confirmation of progression scan is required at no less than 4 weeks and preferably at the next scheduled visit after first overall visit response of progression of disease. Confirmed progression is defined as:

- ≥20% increase in sum diameters of target lesions compared to the nadir at 2 consecutive visits
- And/or significant progression (worsening) of NTLs or NLs at the confirmatory progressive disease timepoint compared with the first timepoint where progression of NTLs or NLs identified
- And/or additional new unequivocal lesions at the confirmatory progressive disease timepoint compared with the first timepoint NLs identified

If progression is not confirmed then the overall visit response should be assessed as SD/PR or CR and the patient should continue scheduled RECIST 1.1 CT/MRI scans. If progression is confirmed the overall visit response should be assessed as progressive disease.

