Accumulating evidence indicates that objective responses to immunotherapy follows delayed kinetics of weeks or months and can be preceded by initial apparent radiological progression or appearance of new lesions (NLs) or some enlarging lesions, while other target lesions are regressing ("mixed response") (50). It is therefore reasonable to allow for these possibilities and continue to treat the patient until progression is confirmed and found to be advancing at the next imaging assessment as per iRECIST. These considerations should be balanced by clinical judgment as to whether the patient is clinically deteriorating and unlikely to receive any benefit from continued treatment.

Such deterioration will be assessed to have occurred after a clinical event that, in the Investigator's opinion, is attributable to disease progression, is unlikely to reverse with continued study treatment and therefore indicates that the patient is not benefiting from study treatment and cannot be managed by the addition of supportive care.

The decision to continue or stop treatment should be discussed with the Medical Monitor and will be documented in the study files.

The maximum duration of the treatment period for each patient within this study may be up to 48 months. Provisions may be made for patients who are still on treatment and receiving benefit at this timepoint.

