#### IRECIST

The continued use of RECIST 1.1 is recommended to define whether tumour lesions, including lymph nodes, are measurable or non-measurable, as well as for the management of bone lesions, cystic lesions, and lesions with previous local treatment (eg. radiotherapy; table 1). Similarly, no changes have been made to the recommendations regarding the method of measurement, although clinical examination and chest radiograph are rarely used, with the availability of more modern imaging techniques (eg. CT scans and MRI). The principles used to establish objective tumour response are largely unchanged from RECIST 1.1, but the major change for iRECIST is the concept of resetting the bar if RECIST 1.1 progression is followed at the next assessment by tumour shrinkage.

iRECIST defines iUPD on the basis of RECIST 1.1 principles; however, iUPD requires confirmation, which is done on the basis of observing either a further increase in size (or in the number of new lesions) in the lesion category in which progression was first identified in (ie, target or non-target disease), or progression (defined by RECIST 1.1) in lesion categories that had not previously met RECIST 1.1 progression criteria. However, if progression is not confirmed, but instead tumour shrinkage occurs (compared with baseline), which meets the criteria of iCR, iPR, or iSD, then the bar is reset so that iUPD needs to occur again (compared with nair values) and then be confirmed (by further growth) at the next assessment for iCPD to be assigned. If no change in tumour size or extent from iUPD occurs, then the timepoint response would again be iUPD. This approach allows atypical responses, such as delayed responses that occur after pseudoprogression, to be identified, further understood, and better characterised (tables 1–3, figure 2, appendix pp 2–4). Sample case record forms and protocol sections are included in the appendix pp 5–19. In the next few paragraphs, we only briefly summarise sections of RECIST 1.1 that are unchanged; readers should refer to RECIST 1.1 for full descriptions.

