## Amended Clinical Trial Protocol 07 KY1044/SAR445256-KY1044-CT01/TCD17370 - alomfilimab

10-Nov-2021 Version number: 1

Seymour et al.

Page 6

disease; iUPD can be assigned multiple times as long as iCPD is not confirmed at the next assessment. Progression is confirmed in the target lesion category if the next imaging assessment after iUPD (4–8 weeks later) confirms a further increase in sum of measures of target disease from iUPD, with an increase of at least 5 mm. However, the criteria for iCPD (after iUPD) are not considered to have been met if complete response, partial response, or stable disease criteria (compared with baseline and as defined by RECIST 1.1) are met at the next assessment after iUPD. The status is reset (unlike RECIST 1.1, in which any progression precludes later complete response, partial response, or stable disease). iCR, iPR, or iSD should then be assigned; and if no change is detected, then the timepoint response is iUPD.

The assessment of non-target lesions at each timepoint follows similar principles iUPD (but not iCPD) can have been documented before iCR or when the criteria for neither CR nor PD have been met (referred to as non-iCPD/non-iUPD) and can be assigned several times, as long as iCPD was not confirmed. iUPD is defined by RECIST 1.1 criteria; however, iUPD can be assigned multiple times as long as iCPD is not confirmed at the next assessment. Progressive disease in the non-target lesion category is confirmed if subsequent imaging, done 4–8 weeks after iUPD, shows a further increase from iUPD. The criteria for iCPD are not judged to have been met if RECIST 1.1 criteria for complete response or non-iCR/non-iUPD are met after a previous iUPD. The status is reset (unlike RECIST 1.1) and iCR, or non-iCR/non-iUPD is assigned; if no change is detected, the timepoint response is iUPD.

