Target lesions: iCR; non-target lesions: non- iCR/non-iUPD; new lesions: no	iPR	iPR
Target lesions: iPR; non-target lesions: non- iCR/non-iUPD; new lesions: no	ipr	iPR
Target lesions: iSD; non-target lesions: non- iCR/non-iUPD; new lesions: no	iSD	iSD
Target lesions: iUPD with no change, or with a decrease from last timepoint; non-target lesions: iUPD with no change, or decrease from last timepoint; new lesions: yes	Not applicable	New lesions confirm iCPD if new lesions were previously identified and they have increased in size (25 mm in sum of measures for new lesion target or any increase for new lesion non-target) or number; if no change is seen in new lesions (size or number) from last timepoint, assignment remains iUPD
Target lesions: iSD, iPR, iCR; non-target lesions: iUPD; new lesions: no	iUPD	Remains iUPD unless iCPD is confirmed on the basis of a further increase in the size of non-target disease (does not need to meet RECIST 1.1 criteria for unequivocal progression)
Target lesions: iUPD; non-target lesions: non- ICR/non-IUPD, or iCR; new lesions: no	iupd	Remains iUPD unless iCPD is confirmed on the basis of a further increase in sum of measures ${\geq}5$ mm; otherwise, assignment remains iUPD
Target lesions: iUPD; non-target lesions: iUPD; new lesions: no	iUPD	Remains iUPD unless iCPD is confirmed based on a further increase in previously identified target lesion iUPD in sum of measures >5 mm or non-target lesion iUPD (previous assessment need not have shown unequivocal progression)
Target lesions: iUPD; non-target lesions: iUPD; new lesions: yes	iupd	Remains iUPD unless iCPD is confirmed on the basis of a further increase in previously identified target lesion iUPD sum of measures ≥5 mm, previously identified non-target lesion iUPD (does not need to be unequivocal), or an increase in the size or number of new lesions previously identified
Farget lesions: non-iUPD or progression; non- arget lesions: non-iUPD or progression; new lesions: yes	iUPD	Remains iUPD unless iCPD is confirmed on the basis of an increase in the size or number of new lesions previously identified

Target lesions, non-target lesions, and new lesions defined according to RECIST 1.1 principles; if no pseudoprogression occurs, RECIST 1.1 and iRECIST categories for complete response, partial response, and stable disease would be the same.

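### Section 6.2.1.2 confirms target-lesion progression with no growth between scans, contrary to Appendix 2, and SAP 8.6.4 omits the Appendix 2 date rule for progression that is never confirmed

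*Protocol*

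**What the plan says.** Protocol Section 6.2.1 names two criteria sets, RECIST 1.1 (Appendix 1) and iRECIST (Appendix 2, the reprinted guideline), and uses both for response analysis and treatment decisions. Section 6.2.1.2 then gives its own definition of confirmed progression. For target lesions it is "≥20% increase in sum diameters of target lesions compared to the nadir at 2 consecutive visits". The other two bullets, on non-target and new lesions, compare the confirmatory scan with the scan that first showed progression. The target-lesion bullet compares both scans with the nadir. The section closes: "If progression is not confirmed then the overall visit response should be assessed as SD/PR or CR".

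Appendix 2 confirms progression in the target category when the next scan, 4 to 8 weeks later, "confirms a further increase in sum of measures of target disease from iUPD, with an increase of at least 5 mm". Otherwise: "If no change in tumour size or extent from iUPD occurs, then the timepoint response would again be iUPD". Its Table 2 gives the same result for target lesions: "Remains iUPD unless iCPD is confirmed on the basis of a further increase in sum of measures" of at least 5 mm. Protocol Section 5.3 tells sites to "continue to treat the patient until progression is confirmed and found to be advancing at the next imaging assessment as per iRECIST".

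For iRECIST PFS, SAP 8.6.4 takes the first iUPD as the event only when the next assessment confirms it as iCPD. No SAP section says how iCPD is assigned. Under its statistical considerations, Appendix 2 has a fallback that SAP 8.6.4 lacks. If progression is never confirmed and no iSD, iPR or iCR follows, the iUPD date still counts when the patient stops as not clinically stable, has no further assessments, stays iUPD throughout, or dies of the cancer.

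**The concern.** The same pair of scans can be recorded as confirmed progression or as iUPD, depending on which protocol text the site follows. iRECIST ORR and PFS are secondary endpoints in both phases, and SAP 8.6.2 has investigators report iUPD and iCPD. Confirmation on a sum that has not grown has three effects:

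- It fixes an iPFS event at the iUPD date, which Appendix 2 would disregard if the patient later reached iSD, iPR or iCR.
- It closes the response window: Appendix 2 Table 1 allows no iCR, iPR or iSD after iCPD, and SAP 8.6.1 counts responses only until progression.
- It may end imaging, because Table 6-3 schedules scans until progression per iRECIST.

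The SAP gap works in the other direction and exists whatever the bullet says. Section 5.3 takes patients with unconfirmed progression and clinical deterioration off treatment and follows them until confirmed progression or new therapy. SAP 8.6.4 censors patients who receive other cancer treatment before progression, at the last evaluable assessment without progression. Such a patient is an event under Appendix 2 and censored under the SAP. That censoring is informative and makes iPFS look longer.

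**Working it through.** The plan states no figure to reproduce, so the check applies both rules to the same sums. All millimetre values and scan days are assumed, since the documents hold no patient data.

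**Confirmation rule.** Let N be the nadir, U the sum at iUPD and S the next sum.

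- Section 6.2.1.2 confirms if S ≥ 1.2N.
- The Appendix 2 target rule confirms if S ≥ U + 5 mm.
- They disagree when 1.2N ≤ S < U + 5 and no other lesion category confirms. The window is U + 5 − 1.2N wide. Taking N ≥ 25 mm makes 20% of N at least 5 mm, so the RECIST 1.1 absolute-increase condition is also met.

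With N = 100 mm, U = 120 gives a window of 120 to <125 mm (5 mm wide), U = 125 gives 120 to <130 mm (10 mm), and U = 140 gives 120 to <145 mm (25 mm).

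Examples with baseline = nadir = 100 mm and no other category progressing:

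| U | S | Change | S vs nadir | 6.2.1.2 | Appendix 2 |
|---|---|---|---|---|---|
| 125 | 121 | −4 mm | +21% | confirmed | iUPD |
| 140 | 121 | −19 mm | +21% | confirmed | iUPD |
| 125 | 128 | +3 mm | +28% | confirmed | iUPD |
| 125 | 130 | +5 mm | +30% | confirmed | iCPD |
| 125 | 118 | −7 mm | +18% | not confirmed | iSD |

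The last two rows mark the limits: the rules agree once growth reaches 5 mm, and again once the sum falls below 1.2N. The third row shows why the closing sentence of 6.2.1.2 must change with the bullet. Under the 5 mm rule 128 mm is unconfirmed, and that sentence would then make a sum 28% above nadir SD, PR or CR.

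**iPFS.** SAP 8.6.4 gives (event or censoring date − first dose date + 1)/30.4375. Scans at weeks 8 and 16 are taken as Days 57 and 113: 57/30.4375 = 1.87 months and 113/30.4375 = 3.71 months.

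- *A: 125 mm on Day 57, then 121 mm, later iSD or better.* Section 6.2.1.2 gives an event at 1.87 months. Appendix 2 drops that event.
- *B: 125 mm on Day 57, then 121 mm at every later scan.* Section 6.2.1.2 and Appendix 2 both give an event at 1.87 months. The 5 mm rule combined with SAP 8.6.4 as written gives no event while the patient is alive. Correcting the bullet alone would therefore lose this event.
- *C: stable on Day 57, iUPD on Day 113, deteriorates, starts new therapy with no confirmatory scan.* Appendix 2 gives an event at 3.71 months. SAP 8.6.4 censors at 1.87 months.

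**The case against.** The bullets follow a sentence framed as specific to this study, and Appendix 2 is a reprinted article, so the body text could be read as the operative rule. That is a fair reading, but no text declares a departure or gives precedence. Section 6.2.1 adopts Appendix 2 without reservation, Section 5.3 asks for advancing progression as per iRECIST, and the two neighbouring bullets do require worsening since the first progression scan.

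Sites are not left without an iUPD option, since SAP 8.6.2 lists it as a category. Which rule they applied cannot be told from the documents.

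The practical effect is small, and this stands. In patient B the body text and Appendix 2 give the same iPFS date. The confirmation rules diverge in outcome mainly when a sum still at least 20% above nadir later recovers.

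A reader might infer three stronger things that the documents do not support:

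- *That patients are wrongly taken off treatment.* Section 5.3 asks for advancing progression and lets patients with confirmed progression continue in their best interest after discussion with the Medical Monitor.
- *That the primary result is exposed.* Phase 2 ORR uses RECIST 1.1.
- *That a sum well below baseline but above nadir resets to a response.* Appendix 2 speaks of "partial response, or stable disease criteria (compared with baseline and as defined by RECIST 1.1) are met at the next assessment after iUPD", which might suggest that baseline 200, nadir 100, iUPD 125 and then 129 mm becomes iPR, because 129 mm is 35.5% below baseline. But that sum is 29% above nadir and growing. The same phrase refers to RECIST 1.1, under which progression in target lesions makes the overall response progression, and Appendix 2 Table 2 keeps target iUPD as iUPD without a 5 mm rise.

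**Conclusion.** Two inconsistencies stand. Section 6.2.1.2 and Appendix 2 disagree on confirming target-lesion progression whenever the next sum is at least 1.2 times nadir but less than 5 mm above the iUPD sum, provided no other category confirms. SAP 8.6.4 omits the Appendix 2 fallback, so some patients with progression that is never confirmed are censored in iPFS or never counted. The second exists under the current bullet and would reach more patients if the bullet alone were corrected.

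The severity is minor. The affected endpoints are secondary and descriptive, with no formal testing, and few patients should change. Appendix 2 puts pseudoprogression below one in ten, mainly from melanoma studies and unclear in other tumours, while the Phase 2 indications of interest are TNBC and HNSCC. The documents give no figure for how often patients start new therapy without a confirmatory scan, so the size of the censoring effect is unknown.

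**What to change.** 1. In SAP 8.6.4, define iCPD as in Appendix 2 and add the fallback. The iUPD date is the event date if iCPD never occurs and no later iSD, iPR or iCR follows, when the patient stops as not clinically stable, has no further assessments, stays iUPD at all later assessments, or dies of the cancer.
2. In Section 6.2.1.2, replace the target-lesion bullet with: *a further increase of at least 5 mm in the sum of target-lesion diameters from the iUPD sum at the next assessment.* Add that RECIST 1.1 progression in another lesion category at that scan also confirms, as Appendix 2 provides.
3. Replace the clause on unconfirmed progression with: *the response is iSD, iPR or iCR only if those criteria, as defined by RECIST 1.1, are met, so that the sum no longer meets progression criteria relative to nadir; otherwise it remains iUPD.* Keep the instruction to continue scheduled scans.
4. List site-reported iCPDs that do not meet the definition on the recorded lesion data.

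If the looser bullet is deliberate, Section 6.2.1.2 should say that it departs from Appendix 2 and takes precedence, and Section 5.3 should be aligned.

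Items 1 and 4 need only a SAP update and one programmed check; SAP 10.5.2.2 already plans listings of target, non-target and new lesions. Items 2 and 3 need a protocol amendment. With the planned clinical end at Q3 2023/Q1 2024 and the latest SAP version dated March 2024, that amendment may change few recorded responses, so the SAP items come first. No extra scans are needed.
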